**C.4.14 Flowchart and Timeline of Procedures for All Aims:**

Procedure	Location	Timing
Consent for participation, screening (physical examination, routine blood work, urinalysis, EKG, metal screening, SCID, ASI, HIV, and urine drug screen)	VCU Collaborative Advanced Research Imaging (CARI) program	Day 1
Training session on the cognitive tasks, mock scan, pre-treatment behavioral performance	MR Imaging Center Mock Scanner at CARI	Day 2
Urine drug screen, urine pregnancy screen, breath alcohol screen	CARI	Day 3
Sagittal and SENSE localizers, 3-D MPRAGE, IMT/DMT fMRI (x 3), Go/NoGo fMRI (x 3), 3D-FLAIR, T2-weighted fast spin echo	CARI Research Dedicated 3T MRI Scanner	Day 3

**C.4.15 *Identical Fmdmgs on MRI:*** The FLAIR images and T2 weighted spm echo images from all subjects will be read by the study Radiologist. The subjects who have clinically significant abnormalities will be excluded from the study and referred for appropriate treatment.

**C.4.16 FMRI Preprocessing:** The fMRI data is preprocessed using Statistical Parametric Mapping (SPM8, <http://www.fil.ion.ucl.ac.uk/spm/>) software from the Wellcome Department of Cognitive Neurology, London, UK, implemented in Matlab (Mathworks Inc.). After slice-timing correction, each fMRI time series is realigned to correct for head motion. Runs with head motion greater than 1 voxel (3.7S mm translation on any axis) or rotation greater than 3.7S degrees are eliminated from analysis. After coregistering the high-resolution 30-MPRAGE to the fMRI images, the 30-MPRAGE is warped to the coordinates of the Montreal Neurological Institute (MNI) standard space [172, 173] using the SPM8 Normalisation procedure, consisting of affine followed by non-linear transformations. These transformations are applied to the fMRI series to convert the fMRI images to MNI space, and the fMRI images are then resliced to 2 mm isotropic resolution and spatially smoothed with a Gaussian filter of 8 mm isotropic full width at half maximum (FWHM).

**C.4.17 SPM univariate analysis of working memory fMRI data:** First-level voxel-wise univariate statistical analysis of the fMRI data is conducted using SPM8. The IMT and DMT blocks for each digit condition are modeled by boxcar functions convolved with the SPM8 canonical hemodynamic response function. The parameters for each condition are estimated using the General Linear Model (GLM) [174] at each voxel without global normalization. The fMRI time series is high-pass filtered with an optimized cut-off period of 330 s determined by the Fourier transformation of each condition's time model, which shows that the signal from the experimental condition is retained at this value but not at shorter cut-offs. Activation for each digit condition is defined as the contrast of DMT minus IMT parameter estimates ("DI") for that digit condition (i.e., 013, DIS, and 017 for 3 digits, S digits, and 7 digit conditions respectively). In addition, the following contrast images are defined to determine the interaction effects between the memory delay (IMT and DMT) and the digit load (3 digits, S digits, and 7 digits): DIS minus 013, 013 minus 015, 017 minus 013, 013 minus 017, 017 minus DIS, and DIS minus 017. The following contrast images are defined to determine the main effects of memory delay (pooled across 3 digits, S digits, and 7 digits): combined 013, DIS, and 017. The summary contrast images are output for each subject for entry into the second-level analysis. Because a between-group DCM study focuses on the characterization of abnormal connectivity in a common network of regions, Seghier et al. [79] recommended that only commonly activated regions in patients and controls should be included as nodes in DCM [79]. Accordingly, a second-level Random Effects [175] SPM8 GLM analysis is conducted in order to determine the nodes of the working memory system that are common to both groups for purpose of DCM analysis. For each type of summary contrast image, the group difference and the main effects across the means for both groups are determined with the default non-sphericity correction for unequal variance between groups. The cluster-defining threshold is voxel  $t = 2.5$ . Statistical significance of the fMRI analysis is false discovery rate (FDR) corrected cluster  $P$  less than 0.05.

**C.4.18 SPM univariate analysis of response inhibition fMRI data:** This processing is similar to that for working memory, except for the following. (a) The cut-off period of the high-pass temporal filter is 128 s, which is an optimized setting determined by Fourier transform of the Go/NoGo task time-series model. (b) The summary contrast images of the first level fixed effects analysis are: correct Easy NoGo trials minus correct Go trials, correct Hard NoGo trials minus correct Go trials, correct Hard NoGo trials minus correct Easy NoGo trials and combined correct NoGo trials (correct Hard NoGo trials plus correct Easy NoGo trials) relative to correct Go trials (in brain regions *not* showing significant interaction of activation with task difficulty). The last contrast image is used to investigate the overall effects of the NoGo trials.

**C.4.19 Effective Connectivity Analysis:** The effective connectivity analysis, described below, is conducted using *stochastic and nonlinear DCM (snDCM)* as implemented in the latest update to SPM8.

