unpublished pilot data (Section C.2.4) have shown that the baseline fMRI working memory activation and the effective connectivity elicited by the working memory task are predictive of treatment outcome with DA enhancing medications in COs. Previous studies have shown that cocaine use can induce impaired response inhibition in both human ([1-8] and see [9] for review) and animals ([10-12] and see [13] for review). In addition, there is evidence ([15-19] and see [20, 21] for review) supporting the hypothesis that DA modulates response inhibition. Furthermore, impulsive personality traits predict DA-dependent changes in frontostriatal activity during component processes of working memory [117]. A study [100] conducted by our group has shown that trait impulsivity is predictive of cocaine addiction treatment outcome. *The relationship between cognitive domains and DA is relevant because the major objective of this study is to predict treatment outcome of DA enhancing medications.*

**Summary of Significance:** (a) Establishing the directional relationship between PFC and striatum and the role of striatal gating in cocaine treatment response will significantly improve our understanding of dopaminergic and pharmacotherapeutic mechanisms in COs. (b) The pilot data (Section C.2.4) suggest that treatment outcome in COs with low pretreatment striatal OA can be improved with OA enhancing treatments by increasing striatal OA function, which we theorize increases striatal gating of cortico-cortico connections. Thus the evidence supporting the hypothesized striatal gating mechanism will have significant implication in cocaine addiction treatment. (c) An issue in cocaine dependence research is the lack of clinically useful biomarkers for pharmacotherapies. Effective connectivity as measured by snOCM may ultimately lead to clinically useful biomarkers for cocaine dependence and its treatment.

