**C.4.9 Task Practice and Mock MRI Simulation:** Prior to the real MRI scan, the subjects undergo at least 10 min of practice of the fMRI tasks until it is clear that the procedures are understood and that the majority of the practice responses are correct. After that, the subjects undergo a mock MRI scan using a Philips product MRI

Simulator. Lying in the mock scanner, the subject performs the fMRI tasks as in the real scan, while listening to a recording of MRI sounds. The fMRI tasks are written in E-Prime 1.2 (Psychology Software Tools).

**C.4.10 Pre-scan Screening:** Immediately prior to the real MRI scan, all subjects undergo urine drug screen and breath alcohol screen. Female subjects also undergo urine pregnancy screen. The subjects with a breath alcohol result of greater-than-zero do not proceed for the MRI scan that day, and are rescheduled. The control subjects with a positive urine drug screen are excluded from the study. The female subjects with a positive urine pregnancy test are excluded from the study. Subjects who regularly smoke tobacco are asked to smoke two hours prior to the first fMRI scan, and not to smoke after that until the fMRI scans are finished.

**C.4.11 MRI Scans:** The MRI session is approximately 90 min, with a 10 min break in the middle. The first 2 series are a T1-weighted spin echo 3-plane localizer (scout), and a SENSE localizer. A high resolution T1-weighted 3D-MPRAGE series is acquired with the following parameters: 256 x 256 acquisition and reconstruction matrix, in-plane resolution= 0.94 mm, 170 sagittal slices, 0.94 slice thickness. This is followed by 3 working memory (IMT/DMT) **and 3 response inhibition (Go-NoGo) fMRI series (runs)** with approximately 2 minutes rest between runs. Each fMRI series is a single shot spin-echo echoplanar (EPI) pulse sequence (see next section for rationale), with SENSE factor= 2.0, repetition time= 2212 ms for IMT/DMT **and 2500 ms for Go-NoGo**, echo time= 75 ms (optimized for spin echo), flip angle= 90 degrees, number of axial slices = 22 for IMT/DMT **and 25 for Go-NoGo**, field-of-view= 240 mm x 240 mm, in-plane resolution 3.75 mm x 3.75 mm, slice thickness= 3.75 mm, gap= 1.25 mm, repetitions= 294 for IMT/DMT **and 256 for Go-NoGo** after 10 dummy acquisitions, total duration = 10 min 47 s for IMT/DMT **and 10 min 40 s for Go-NoGo**. A 3D-FLAIR and T2-weighted fast spin echo are acquired to rule out incidental intracranial findings.

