*Volumes of interest (VOIs) and time series extraction:* We follow the method of constructing the VOIs as described in Ma et al. [138]. The significant group level activation clusters form the VOIs, which are further constrained [141] to be within the boundaries of the aforementioned seven ROIs, as defined by anatomical atlases. The atlas-derived binary masks of the regions are obtained from the Anatomical Automatic Labeling atlas [180] as implemented in the WFU (Wake Forest University) PickAtlas SPM toolbox [181, 182]. The binary mask of DLPFC is the middle frontal gyrus. The binary mask of IFC is the set-theoretic union of the atlas-based binary masks of inferior frontal gyrus pars opercularis and inferior frontal gyrus pars triangularis. The binary mask of PPC is the union of the atlas-based binary masks of superior parietal lobule and inferior parietal lobule. The binary mask of dorsal striatum is the union of the atlas-based binary masks of dorsal caudate and dorsal putamen, and the binary mask of ventral striatum is the union of the atlas-based binary masks of ventral caudate, ventral putamen, and nucleus accumbens. Following Postuma and Dagher [183],  $z = 7$  mm (Talairach space) is used as the border between dorsal caudate and ventral caudate, and  $z = 2$  mm (Talairach space) is used as the border between dorsal putamen and ventral putamen. The atlas-derived binary mask of the nucleus accumbens is obtained from the Harvard-Oxford Subcortical Structural atlas (<http://www.cma.mgh.harvard.edu/>) as provided in the FSL software [184]. Each VOI is obtained by the intersection of the atlas-based binary masks with the significant activation clusters in common for both groups, as determined by the SPM8 second level random effects univariate analysis. For each subject, the time series from the first-level univariate analysis for that subject is extracted from all voxels within the VOI, and the principal eigenvariate [141] of this time series, which is adjusted for effects of interest, is input into DCM for model estimation [141]. The same VOIs are used for all subjects.

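### Beyond realignment and a one-voxel run exclusion, the plan does not control head motion or unequal run numbers, which could bias Aim 1 and the gating–TES slope in Aim 2

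*Protocol*

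**What the plan says.** - **Preprocessing (protocol C.4.16).** "each fMRI time series is realigned to correct for head motion". The exclusion rule follows: "Runs with head motion greater than 1 voxel (3.7S mm translation on any axis) or rotation greater than 3.7S degrees are eliminated from analysis". The characters 3.7S are a text-reading slip for 3.75, since C.4.11 gives "in-plane resolution 3.75 mm x 3.75 mm, slice thickness= 3.75 mm".
- **First-level model, working memory (C.4.17).** "The IMT and DMT blocks for each digit condition are modeled by boxcar functions convolved with the SPM8 canonical hemodynamic response function". The section also gives a 330 s high-pass cut-off and rules out global normalisation. It lists no realignment parameter or other motion term.
- **First-level model, Go/NoGo (C.4.18).** "This processing is similar to that for working memory, except for the following". The exceptions are the filter cut-off and the contrasts.
- **Input to DCM (C.4.19.1).** The principal eigenvariate of each region, "which is adjusted for effects of interest, is input into DCM for model estimation".
- **Group models (C.4.20 and SAP).** The TES regression contains treatment, gating and their interaction. The confounder rule names pretreatment task performance and demographic variables. The covariates of the Aim 1 ANCOVA are not listed.
- **Runs (C.4.11, C.4.16).** Three runs are acquired per task and runs are dropped one at a time. There is no minimum number and no rule for a subject left with one or two.
- **Other provisions.** Before the real scan (C.4.9), "the subjects undergo a mock MRI scan using a Philips product MRI" simulator. C.4.1 allows for 20% unusable scans per group and names head motion among the causes.

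**The concern.** Realignment corrects the estimated rigid-body displacement. Signal changes caused by movement can remain, and they can reach several regions in the same volumes. DCM interprets the joint behaviour of those regions as coupling. If cocaine-dependent subjects and controls differ in how much they move, part of the Aim 1 comparison may reflect motion.

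In Aim 2 gating is measured, not randomised, so anything related to both the gating estimate and TES confounds the slope between them. Section A.6 reports that "trait impulsivity is predictive of cocaine addiction treatment outcome". Whether impulsive patients also move more in the scanner is an assumption, since the documents do not say.

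Run loss is a second route. A subject with one surviving run has a less precise estimate, on which priors and simpler models carry more weight. If run loss is related to group or outcome, so is the distortion. Aim 3 uses essentially the same analysis for Go/NoGo and inherits both problems.

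At stake is the biomarker claim. Without motion terms, a reader could not separate a connectivity finding from a motion finding.

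**Working it through.** **1. The plan's own figures.** Recruitment: 24/(1 − 0.20) = 30 per group, as in C.4.1. Aim 2 power (C.4.21: r = 0.60, n = 24, two-sided 0.05): the pilot correlation was Spearman, so use Fisher's z with variance 1.06/(n − 3). Then atanh(0.60) × √(21/1.06) − 1.96 = 0.693 × 4.451 − 1.96 = 1.125, which gives 87.0%. Simulation of the Spearman test gives 85.0%. The stated 86% is reproduced. Aim 1 power at d = 1.89 with 24 per group exceeds 99.9%, as stated. The 20% allowance is for unusable scans; it does not deal with subjects who lose only some runs.

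**2. Following motion through the pipeline.** After the exclusion rule, the first-level models contain task regressors and a high-pass filter. Adjusting the eigenvariate for effects of interest can remove only nuisance terms that the model contains, and no motion term is among them. Motion is outside the confounder rule and absent from the TES regression. For the Aim 1 ANCOVA the text is silent.

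**3. Illustration of confounding in the gating–TES slope (assumed values).** Let motion correlate a with gating and b with TES, with no true gating–TES relation. The spurious correlation is a × b. The rejection rate of a nominal 5% test at n = 24 uses Fisher's z with SE 1/√21.

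| Size of a | Size of b | Size of spurious r | Rejection rate |
|---|---|---|---|
| 0.2 | 0.2 | 0.04 | 5.4% |
| 0.3 | 0.3 | 0.09 | 7.0% |
| 0.3 | 0.5 | 0.15 | 10.7% |
| 0.5 | 0.5 | 0.25 | 21.6% |

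The sign of the spurious correlation is the sign of a × b. It is negative, like the pilot relation (r = −0.69, C.2.4), if motion raises the gating estimate and goes with lower TES. It is positive if motion lowers both.

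**4. Illustration of run loss (assumed single-run reliability R₁).** Spearman–Brown gives R_k = kR₁/(1 + (k − 1)R₁). With r = 0.60 for three runs, r_k = 0.60 × √(R_k/R₃). All subjects are taken to have the same k, and power uses the Spearman variance at n = 24.

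| R₁ | R for 3 / 2 / 1 runs | r | Power |
|---|---|---|---|
| 0.3 | 0.56 / 0.46 / 0.30 | 0.60 / 0.54 / 0.44 | 87% / 77% / 55% |
| 0.5 | 0.75 / 0.67 / 0.50 | 0.60 / 0.57 / 0.49 | 87% / 81% / 67% |
| 0.7 | 0.88 / 0.82 / 0.70 | 0.60 / 0.58 / 0.54 | 87% / 84% / 76% |

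This is loss of precision. Bias needs run loss to be related to group, gating or outcome. In a simple linear model with a zero-centred prior (also assumed), the R₁ = 0.5 row gives the weights on the data: 0.50/0.75 = 0.67, so a one-run estimate is one third closer to zero than a three-run estimate. That lowers positive values and raises negative ones.

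**5. The interaction.** The MRI session precedes treatment (C.4.4), so motion is balanced between arms in expectation. A motion–TES relation common to both arms multiplies expected TES by the same function of gating in each arm. It therefore cancels from the treatment-by-gating term on the log scale.

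**The case against.** A reader might infer from the exclusion rule that motion is handled only by deleting runs and that up to 3.75 mm of movement stays in the data. The documents do not support this. Every series is realigned first, so 3.75 mm is a ceiling on displacement before correction. What can remain is residual motion-related signal, which the documents do not quantify.

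A reader might also infer that motion would manufacture the hypothesised results. Plausible mechanisms point the other way. Shared artefact in patients would tend to raise their apparent coupling, whereas the pilot found it lower (−0.025 Hz against 0.019 Hz). If restless patients lost runs, had low gating estimates for that reason and did worse, the result would oppose the pilot relation, in which low gating went with better TES. This stands: the direction is open, and masking is as much a risk as a false positive.

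Further points in the plan's favour:
- C.4.20 and the SAP call the treatment-by-gating interaction the critical element, and randomisation largely protects it.
- Impulsivity is balanced by the urn scheme and is a planned subgroup variable. Balance between arms, however, does not remove confounding of a slope within an arm.
- Section A.4 says stochastic DCM allows for random neuronal and vascular fluctuations. The plan does not claim that this removes artefact shared across regions.
- Practice and the mock scan may reduce motion, but they do not adjust for what is left.
- The ANCOVA covariates are unlisted, so the lack of a motion term there is silence and not a stated exclusion.

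**Conclusion.** The point holds as a gap in method that is cheap to close. Following the plan as written leaves residual motion-related signal in the DCM input and lets run number vary between subjects without adjustment. The exposed analyses are the patient-control connectivity comparison (Aim 1), gating as a predictor of TES (Aim 2), and their Go/NoGo counterparts (Aim 3).

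The size is not known from the documents. The rejection rates of 5% to 22% and the power losses in the working rest on assumed correlations and reliabilities, and they concern a simple correlation, not a DCM parameter. Bias further requires motion or run loss to be related to group, or to both gating and TES, and the documents give no data on either. The treatment-by-gating interaction would be confounded only if motion modified the drug effect. No stated sample-size or power figure is wrong on this account.

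**What to change.** 1. **C.4.17 and C.4.18:** add the six realignment parameters to each first-level model as nuisance regressors, so that the extracted eigenvariate is motion-adjusted.
2. **C.4.20 and the SAP:** compare mean framewise displacement and number of usable runs between groups. Add both to the existing confounder rule, as sensitivity covariates in the Aim 1 ANCOVA and the TES model. Fit the TES sensitivity model whether or not the arms differ on them, because confounding of the gating slope does not need an arm difference.
3. **Both documents:** repeat the main analyses in subjects with all three runs for the task, and report how many subjects have one, two and three.

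No new data are needed, since realignment already yields the parameters. The cost is about 6 degrees of freedom per run out of 294 volumes (6/294 = 2.0%) or 256 (6/256 = 2.3%), and some loss of task signal where movement is locked to the task. The sensitivity models carry up to two more covariates with about 48 subjects (24 per arm), in a setting that the plan already calls likely underpowered for the interaction. That is why motion and run count belong in sensitivity models and not in the main TES model.

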#### **C.4.19.1 Working memory DCM analysis**

***Regions-of-interest (ROIs):*** L IFC, L DLPFC, L PPC, R PPC, LR dorsal striatum, LR ventral striatum, and LR thalamus are the ROIs. The LR dorsal striatum (or LR ventral striatum) is treated as a single ROI because we found that the DCM parameters on the connections from or to the striatum were similar for left and right striatum [37]. The ROIs are based on the following criteria: (a) these regions showed significant activation in the SPM second-level analysis of the main effect of memory delay for the combined groups in our previous study [37]; (b) meta-analyses have shown that these regions activate consistently during working memory tasks [176, 177]; (c) these regions have been implicated in working memory processes, e.g., encoding [178], storage [179], maintenance [177-179], and executive control [179]; and (d) some regions (e.g., thalamus) have been implicated in treatment response in COs [38].

*Volumes of interest (VOIs) and time series extraction:* We follow the method of constructing the VOIs as described in Ma et al. [138]. The significant group level activation clusters form the VOIs, which are further constrained [141] to be within the boundaries of the aforementioned seven ROIs, as defined by anatomical atlases. The atlas-derived binary masks of the regions are obtained from the Anatomical Automatic Labeling atlas [180] as implemented in the WFU (Wake Forest University) PickAtlas SPM toolbox [181, 182]. The binary mask of DLPFC is the middle frontal gyrus. The binary mask of IFC is the set-theoretic union of the atlas-based binary masks of inferior frontal gyrus pars opercularis and inferior frontal gyrus pars triangularis. The binary mask of PPC is the union of the atlas-based binary masks of superior parietal lobule and inferior parietal lobule. The binary mask of dorsal striatum is the union of the atlas-based binary masks of dorsal caudate and dorsal putamen, and the binary mask of ventral striatum is the union of the atlas-based binary masks of ventral caudate, ventral putamen, and nucleus accumbens. Following Postuma and Dagher [183],  $z = 7$  mm (Talairach space) is used as the border between dorsal caudate and ventral caudate, and  $z = 2$  mm (Talairach space) is used as the border between dorsal putamen and ventral putamen. The atlas-derived binary mask of the nucleus accumbens is obtained from the Harvard-Oxford Subcortical Structural atlas (<http://www.cma.mgh.harvard.edu/>) as provided in the FSL software [184]. Each VOI is obtained by the intersection of the atlas-based binary masks with the significant activation clusters in common for both groups, as determined by the SPM8 second level random effects univariate analysis. For each subject, the time series from the first-level univariate analysis for that subject is extracted from all voxels within the VOI, and the principal eigenvariate [141] of this time series, which is adjusted for effects of interest, is input into DCM for model estimation [141]. The same VOIs are used for all subjects.

*Striatal gating DCM:* Based on Landau et al. [64] showing that striatal DA function is related to working-memory capacity and activation in left inferior PFC, and Honey et al. [185] showing that working memory capacity is related to effective connectivity from L IFC to L PPC, we use L IFC and L PPC as the prefrontal and posterior regions, respectively, in the striatal gating model proposed by O'Reilly and Frank [22]. The activity in the dorsal striatum is hypothesized to gate the connectivity via thalamus, between the L IFC and the L PPC, based on the striatal gating models [22, 23] and our pilot study results (section C.2.4).

**C.4.19.2 Response Inhibition DCM analysis.** ROIs are: R bilateral OFC, LR pre-supplementary motor area (pre-SMA), R PPC, LR dorsal striatum, LR ventral striatum, and LR thalamus are the ROIs, which are based on our pilot data (Section C.2.5); and consistent with: (a) existing striatal gating models [22, 23] and theoretical models on impulsivity [24-26, 186]; (b) review articles on Go-NoGo fMRI studies [27-30] and cocaine addiction Go-NoGo fMRI studies [7, 8, 31, 187, 188]; and (c) DA modulation effect on response inhibition [15]. Except for the striatum, our proposed ROIs are different from those used in a published effective connectivity study [188] using Go/NoGo task, possibly due to different subject samples (children were studied in [188] and we studied adults) and different fMRI design (a block design was used in [188] and we used event-related design). Since these regions are based on our pilot data, other regions, if they show significant activation on fMRI using the larger sample size that is proposed in the grant, will be considered as ROIs in the future. *VOIs and time series extraction:* This part of processing is essentially same as that in the working memory DCM analysis. *Striatal gating DCM:* Based on the study [83] showing significant correlation between dopamine 02 receptor function and glucose metabolism in orbitofrontal cortex, and the study [15] showing that levodopa affected the magnitude of Go/NoGo task-elicited fMRI response in right parietal cortex, we use R lateral OFC and R PPC as the prefrontal and posterior regions, respectively, in the striatal gating models [22, 23]. The activity in the dorsal striatum is hypothesized to gate, via thalamus, the connectivity between the R lateral OFC and the R PPC, based on the striatal gating models [22, 23].

**C.4.19.3 Inference on DCM model structure:** In DCM analysis, the number of candidate DCMs, after permutation and combination of possible endogenous connections and exogenous inputs, is very large. Therefore, the network discovery technique (NDT) [189], as implemented in the latest release of DCM, is used as a first step to determine the model structure for each subject. The NDT scores the relative posterior probability of each candidate DCM in order to evaluate efficiently the large number of possible DCMs and to find the optimal model for each subject. The initial full model to be reduced by NDT includes all possible bi-directional endogenous connections between each node (see C.4.19.1 and C.4.19.2 VOIs). The contextual conditions of the cognitive tasks are putative exogenous inputs and bilinear modulators at each connection in the initial full model. In addition, nonlinear gating by dorsal striatum on PFC-PPC is hypothesized in the initial full model (see section C.4.19.1 and C.19.2). The NDT results for each subject are checked first to see

whether the causal (directional) relationship between the OLPFC and the striatum has been determined and whether the striatal gating OCM is optimal for all subjects in each group. The inference on model structure is further conducted using Bayesian model selection (BMS) [190] and Bayesian family level inference (BFLI) [191], as described in detail in Ma, et al. [138]. BMS is an established procedure for selecting an optimal OCM from alternative OCMs. This is realized by comparing model evidence, which simultaneously quantifies how accurately a model explains the data and model complexity [190]. An "optimal" model is reflected by the Bayesian exceedance probability [190], which denotes the probability that a model is more likely to have generated the observed data than the other models considered. BFLI is an extension of BMS that can be used to select the optimal family from candidate families of models [138, 191].

**C.4.19.4 Inference on DCM parameters:** The inference on OCM parameters is conducted using Bayesian model averaging (BMA) [191]. BMA is a Bayesian approach that averages each OCM parameter across subjects and across models such that the contribution of each model (of each subject) for that parameter is weighted by each model's posterior probability for that subject. Thus, BMA avoids the rigid assumption of an identical single OCM for all subjects that is required in classical "Frequentist" analysis of OCM parameters [191]. The same model space, comprised of the optimal OCM for the COs group plus the optimal OCM for the control group, is used in the BMA analysis of each group to determine the posterior distribution of each OCM parameter for each subject within the group [138].

